10. ANALYSIS OF EFFICACY DATA

All analyses will be based on the FAS for the groups from the start of REN001-202 and from the start of REN001-201 unless stated otherwise.

Missing data will be handled using the complete case methodology described in [Section 8.3.1](#).

As the nDNA-PMM subjects will only be recruited from a subset of the REN001-202 sites, summaries may also be presented only including mtDNA-PMM subjects from the same sites. Two separate sets of subjects may be used: the subjects who received mavodelpar in REN001-201 with their data from the start of REN001-201, and the subjects who received placebo in REN001-201 from the start of REN001-202. Consideration will be given to the duration of exposure for nDNA-PMM subjects when summarising the data from the mtDNA-PMM subjects (e.g., if the duration of exposure of nDNA-PMM subjects is up to 6 months, only the first 6 months of data for the mtDNA-PMM subjects will be used).

10.1. 12-MINUTE WALK TEST (12MWT)

Observed, change from baseline and percent change from baseline values will be summarized by visit using descriptive statistics. The associated 95% confidence intervals for the observed, change from baseline and percent change from baseline means will also be presented. The number of subjects withdrawn prior to the visit or with missing data will also be presented. Note missing data will include those subjects who prematurely stop the 12MWT and their reason for stopping is adjudicated as not being possibly related to the subject's PMM or study treatment.

Mean plots for observed, change from baseline and percent change from baseline values, with 95% confidence intervals will be presented by group with visit on the x-axis. A reference line for no change (i.e., $y=0$) will be included in the change from baseline and percent change from baseline plots.

Spaghetti plots for the changes from baseline will be plotted over time. The plots will be split by group. The y-axis will be uniform across the plots to allow comparisons. A reference line for no change (i.e., $y=0$) will be included.

The impact of the subgroups (specified in [Section 8.5](#)) on the 12MWD will also be investigated descriptively. Summaries will be presented by subgroup.

The number of stops and the number of falls will be summarized by visit. If a subject does not walk for the full 12 minutes, then this will be counted as an additional stop when summarizing.

All data will be listed together with changes from baseline (from start of REN001-202 and from start of REN001-201) and corresponding percent changes from baseline. Assessments

which were prematurely stopped and adjudicated as being at least possibly related to the subject's PMM will be identified. The pre and post exercise measurement for heart rate, blood pressure and RPP scale score will be listed separately, along with their changes from pre-test.

12MWD values, mean, median, minimum and maximum will all be presented to 2 decimal places and SD will be presented to 3 decimal places.

10.1.1. 6-Minute Walk Distance (Derived from 12MWD)

The first and last 6-minute walk distances derived from the 12MWD will be presented in the same way as the 12MWD. Note that if a subject's 12MWD is incomplete but they walk for longer than 6 minutes then only the last 6-minute period will be classified as incomplete.

In addition to the summary presentation, mean plots for observed, change from baseline and percent change from baseline values, with 95% confidence intervals will be presented by group and 6-minute time period with visit on the x-axis. A reference line for no change (i.e., $y=0$) will be included in the change from baseline and percent change from baseline plots.

6-minute walk distance values, mean, median, minimum and maximum will all be presented to 2 decimal places and SD will be presented to 3 decimal places.

10.2. MODIFIED FATIGUE IMPACT SCALE (MFIS)

Observed, change from baseline and percent change from baseline values will be summarized by visit using descriptive statistics, for the subscale scores and total score. The associated 95% confidence intervals for the observed, change from baseline and percent change from baseline means will also be presented. The number of subjects withdrawn prior to the visit or with missing data will also be presented.

Mean plots of observed, change from baseline and percent change from baseline values, with 95% confidence intervals will be presented by group with visit on the x-axis. A reference line for no change (i.e., $y=0$) will be included in the change from baseline plot.

Spaghetti plots for the changes from baseline will be plotted over time. The plots will be split by group. The y-axis will be uniform across the plots to allow comparisons. A reference line for no change (i.e., $y=0$) will be included.

Categorical shift tables of change from baseline showing improvement (at least a 4-point decrease in score), no change (less than a 4-point change in either direction) or worsening (at least a 4-point increase in score) at each visit will be summarized. The table will include categories for withdrawn and missing. Percentages will not be presented for the withdrawn and missing rows, and the percentages presented will use the number of non-

missing values as the denominator. In addition, to account for subjects at the extreme ends of the scale, the shift table will also include the percent improving or worsening based on those subjects who have the potential to improve or worsen respectively.

10.3. PATIENT GLOBAL IMPRESSION OF CHANGE (PGIC) – MUSCLE SYMPTOMS AND FATIGUE SYMPTOMS

PGIC muscle symptoms and fatigue symptoms scores will be summarized by visit as a categorical variable. The table will include categories for withdrawn and missing. Percentages will not be presented for the withdrawn and missing rows, and the percentages presented will use the number of non-missing values as the denominator.

Stacked bar charts will be presented for the proportion of subjects at each of the PGIC scores by visit for each of the groups. The categories will include each of the PGIC levels and missing and withdrawn.

10.4. PATIENT GLOBAL IMPRESSION OF SEVERITY (PGIS) SCORE - MUSCLE SYMPTOMS AND FATIGUE SYMPTOMS

Categorical shift tables from baseline at each visit will be summarized including marginal totals. The table will include categories for withdrawn and missing. Percentages will not be presented for the withdrawn and missing rows, and the percentages presented will use the number of non-missing values as the denominator. In addition, to account for subjects at the extreme ends of the scale, the shift table will be repeated for improvement or worsening from baseline at each visit, based on those subjects who have the potential to improve or worsen, respectively.

Stacked bar charts will be presented for the proportion of subjects at each of the PGIS scores by visit for each of the groups. The categories will include each of the PGIS levels and missing and withdrawn.

10.5. PATIENT-REPORTED OUTCOMES MEASUREMENT INFORMATION SYSTEM (PROMIS) SHORT FORM – FUNCTIONAL ASSESSMENT OF CHRONIC ILLNESS THERAPY (FACIT) FATIGUE 13A

Observed and change from baseline values will be summarized by visit using descriptive statistics for the T-score. The associated 95% confidence intervals for the observed and change from baseline means will also be presented. The number of subjects withdrawn prior to the visit or with missing data will also be presented.

Mean plots of observed and change from baseline values for the T-score, with 95% confidence intervals will be presented by group with visit on the x-axis. A reference line for no change (i.e., $y=0$) will be included in the change from baseline plot.

Spaghetti plots for the changes from baseline will be plotted over time. The plots will be split by group. The y-axis will be uniform across the plots to allow comparisons. A reference line for no change (i.e., $y=0$) will be included.

Categorical shift tables of change from baseline for T-score showing improvement (at least a 5-point decrease in score), no change (less than a 5-point change in either direction) or worsening (at least a 5-point increase in score) at each visit will be summarized. The table will include categories for withdrawn and missing. Percentages will not be presented for the withdrawn and missing rows, and the percentages presented will use the number of non-missing values as the denominator. In addition, to account for subjects at the extreme ends of the scale, the shift table will also include the percent improving or worsening based on those subjects who have the potential to improve or worsen respectively.

10.6. 36 ITEM SHORT FORM SURVEY (SF-36)

Observed and change from baseline values will be summarized at each visit using descriptive statistics for the 8 scale scores. The associated 95% confidence intervals for the observed and change from baseline means will also be presented. The number of subjects withdrawn prior to the visit or with missing data will also be presented.

Mean plots of observed and change from baseline values, with 95% confidence intervals will be presented by group with visit on the x-axis. A reference line for no change (i.e., $y=0$) will be included in the change from baseline plot.

Categorical shift tables of change from baseline for each scale score showing improvement (at least a 4-point increase in score), no change (less than a 4-point change in either direction) or worsening (at least a 4-point decrease in score) at each visit will be summarized. The table will include categories for withdrawn and missing. Percentages will not be presented for the withdrawn and missing rows, and the percentages presented will use the number of non-missing values as the denominator. In addition, to account for subjects at the extreme ends of the scale, the shift table will also include the percent improving or worsening based on those subjects who have the potential to improve or worsen respectively. Where a 4-point change in score indicates an improvement or worsening, subjects with the potential to improve will have a baseline score of 96 or below; similarly, for those with a potential to worsen they will have a baseline score of 4 or more.

Scale scores and changes from baseline will be listed separately from the raw data.

Scale score values will be presented to 0 decimal places.

10.7. BRIEF PAIN INVENTORY

Observed and change from baseline values will be summarized at each visit using descriptive statistics for the pain severity and pain interference scores. The associated 95% confidence intervals for the observed and change from baseline means will also be presented. The number of subjects withdrawn prior to the visit or with missing data will also be presented.

Mean plots of observed and change from baseline values, with 95% confidence intervals will be presented by group with visit on the x-axis. A reference line for no change (i.e., $y=0$) will be included in the change from baseline plot.

Categorical shift tables of change from baseline for pain severity and pain interference showing improvement (at least a 1.5-point decrease in score), no change (less than a 1.5-point change in either direction) or worsening (at least a 1.5-point increase in score) at each visit will be summarized. The table will include categories for withdrawn and missing. Percentages will not be presented for the withdrawn and missing rows, and the percentages presented will use the number of non-missing values as the denominator. In addition, to account for subjects at the extreme ends of the scale, the shift table will also include the percent improving or worsening based on those subjects who have the potential to improve or worsen respectively.

Pain severity and pain interference scores and changes from baseline will be listed with the raw data.

10.8. WORK PRODUCTIVITY AND ACTIVITY IMPAIRMENT QUESTIONNAIRE: SPECIFIC HEALTH PROBLEMS (WPAI: SHP)

WPAI scores, except percent activity impairment, will only be summarized for those subjects who are employed. Observed and change from baseline values will be summarized by visit using descriptive statistics for the 4 WPAI scores. The associated 95% confidence intervals for the observed and change from baseline means will also be presented. The number of subjects withdrawn prior to the visit or with missing data will also be presented.

Mean plots of observed and change from baseline values, with 95% confidence intervals will be presented by group with visit on the x-axis. A reference line for no change (i.e., $y=0$) will be included in the change from baseline plot.

WPAI score values will be presented to 0 decimal places.

10.9. PMM PHENOTYPIC DESCRIPTION

Categorical shift tables from baseline at each visit will be summarized, including marginal totals, for the 3 phenotypic questions. The table will include categories for withdrawn and

missing. Percentages will not be presented for the withdrawn and missing rows, and the percentages presented will use the number of non-missing values as the denominator.

11. ANALYSIS OF PHARMACOKINETIC ENDPOINTS

The mavodelpar concentrations will be evaluated using the PK set. Mavodelpar concentrations will be summarized at each Month 3 scheduled time point using descriptive statistics, including the additional summary statistics geometric mean and geometric CV%. The summary will be repeated for subjects who have completed the 24 h profile. For post-dose samples, only concentrations collected within a 10% window of the protocol specified post dose time point will be included. Similarly, pre-dose concentrations will only be included if the samples were taken prior to dosing on the day. The number of subjects with a BLQ value will also be tabulated.

Linear and log-linear individual concentration profile spaghetti plots against time will be produced for Month 3. All subjects will be displayed on the same plot and mutational genotype (m.3243A>G, m.8344A>G, mt deletion or Other) will be identified for mtDNA-PMM subjects as well as identifying nDNA-PMM subjects. The actual sampling time will be used on the x-axis with pre-dose fixed at zero for all subjects.

Linear and log-linear median concentration profile plots against time will be produced for Month 3. The plots will be repeated for subjects who have completed the 24 h profile. The nominal sampling time will be used on the x-axis. The number of subjects contributing to each time point will be included on the plots. Lines will be included for all subjects and by mutational genotype.

A listing of all REN001-202 concentration data will be presented. The actual time post dose, deviation and percent deviation from nominal post dose time will also be listed for the post dose samples on Day 1 and Weeks 12 and 24. For all other visits the actual time relative to dose the sample was collected will be listed.

Month 3 PK parameters will be summarized for subjects recruited under protocol version 1.0 using descriptive statistics. C_{trough} , C_{max} , and AUC_{τ} will include the additional summary statistics of geometric mean, geometric CV% and CV%; and for T_{max} only the summary statistics median, minimum and maximum will be presented. PK parameters will be listed.

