5.3 Administration

Subjects will receive once daily 100mg REN001 as 2 x 50mg capsules for oral administration for the duration of the study. Study drug should be taken with food at a convenient time to the subject (ideally in the morning). Subjects will be supplied with a dose record card and will be requested to record the date and time of dosing for all study visit days.

At the Month 3 visit, PK samples will be taken pre and post study drug administration over a 4-hour period ([Section 6.3](#)). At this visit the subject should take the study drug at the study centre with food when instructed to do so by the site staff.

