7.7 PK Blood Samples

Blood samples for determination of REN001 concentrations and possibly REN001 metabolite concentrations will be collected via a direct venipuncture or indwelling cannula. A 4.0 ml blood sample, to provide approximately 2 ml of plasma for PK analysis, will be collected into a labelled tube. Sample handling instructions are provided in the REN001-202 Laboratory Manual. The plasma samples will be stored at the central laboratory prior to analysis. Plasma samples will be transferred to the bioanalytical laboratory on dry ice to maintain frozen conditions. Analysis of REN001 concentrations in plasma will be performed using a validated analytical method.

Subjects will be supplied with a dose record card and will be requested to record the date and time of dosing for all study visit days. At each of the Baseline and Month 1 visits a single PK sample will be taken. At Months 6, 12, 18 and 24 two plasma samples will be taken for PK analysis of REN001, sample 1 to be taken on arrival at site, sample 2 to be taken at end of visit. At the Month 3 visit, PK samples will be taken pre and post study drug administration over a 4-hour period (pre-dose and at 1, 2 and 4 hours post dose ([Section 6.3](#))); The subject should take the study drug at the study centre with food when instructed to do so by the site staff, time of dose and time of all PK samples should be recorded.

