3.5. DETERMINATION OF SAMPLE SIZE

The sample size for this study is not based on statistical justification. Recruitment of mtDNA-PMM subjects will be limited to those subjects who participated in REN001-201 or REN001-101, and reside in countries where this long-term safety study is approved. It is estimated that approximately 150 mtDNA-PMM subjects will be enrolled.

It is anticipated that up to 50 nDNA-PMM subjects may also be enrolled.

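### The time of the dose before a PK visit is never recorded, and SAP section 11 sets no limit on time since that dose for the Month 3 pre-dose sample

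*SAP*

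**What the plan says.** **Time of dosing.** Protocol section 5.3 and SAP section 3.7 leave the hour to the subject, with food. Morning is a preference. The SAP makes exceptions only for the Baseline and Month 3 visits.

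**Recording.** Subjects get a dose record card and "will be requested to record the date and time of dosing for all study visit days" (Protocol section 5.3; section 7.7 repeats this). Compliance is by capsule count (section 5.7), which cannot date a single dose.

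**Sampling.** At Month 3 (section 6.3) a sample is drawn, the subject is dosed on site, and further samples follow at 1, 2 and 4 hours. The reminder given at Month 1 (section 6.2) covers dosing at the centre and is silent on the previous day's dose. At Months 6, 12, 18 and 24 the subject doses at the usual time and gives two samples, "sample 1 to be taken on arrival at site, sample 2 to be taken at end of visit" (section 7.7). Month 1 has a single sample, also with dosing at the usual time.

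**Analysis.** SAP section 11 summarises concentrations at Month 3 only. For post-dose samples, "only concentrations collected within a 10% window of the protocol specified post dose time point will be included". For the pre-dose sample, the sole condition is that "pre-dose concentrations will only be included if the samples were taken prior to dosing on the day". Individual plots put every pre-dose value at time zero, and median plots use nominal time. Elsewhere the plan is a listing: "For all other visits the actual time relative to dose the sample was collected will be listed".

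**The concern.** A pre-dose value on once-daily treatment is naturally read as a level about 24 hours after the last dose. Nothing in the plan ensures or checks that. A subject who usually doses in the evening arrives at a daytime Month 3 visit about 12 hours after the last dose; one who missed that dose arrives at about 48 hours. Both pass the inclusion rule, and the planned plots cannot show the difference.

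For subjects recruited under Protocol Version 2.0, Month 3 sampling stops at 4 hours (SAP sections 3.2.3 and 5). nDNA-PMM subjects became eligible only with that version. For them the pre-dose sample is the only Month 3 information on the end of the dosing interval.

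At Months 6 to 24, which carry the long-term exposure data, a sample drawn on arrival may precede that day's dose. So may the end-of-visit sample if the subject doses in the evening. The listing is to give time relative to dose, but the preceding dose is not among the times requested. SAP section 5 sends these data to a population PK analysis, where time since last dose is a basic input. The feeder study was tighter: the notes to SAP Appendix 2 specify that its single samples be taken post-dose, with dose date and time recorded.

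**Working it through.** The plan states no figure on this point, so there is none to reproduce. The check is a count of samples and an illustration of size.

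**1. Samples under the current schedule** (Protocol sections 6.2 to 6.9 and 7.7), post-baseline:

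- Month 1: 1
- Month 3: 4 (pre-dose, 1, 2 and 4 h)
- Months 6, 12, 18 and 24: 4 × 2 = 8
- Total: 1 + 4 + 8 = 13

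**2. Samples that can precede that day's dose.**

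- Evening doser at daytime visits, worst case: 1 (Month 1) + 1 (Month 3 pre-dose) + 8 (Months 6 to 24) = 10 of 13.
- Morning doser: usually only the Month 3 pre-dose sample, which then lies near 24 hours unless a dose was missed.

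Version 1.0 subjects gave 8 samples at Month 3 (pre-dose, 1, 2, 4, 6, 8, 12 and 24 h), so their total is 1 + 8 + 8 = 17.

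**3. Effect on one value.** The documents give no half-life, so t½ is an assumed range. With mono-exponential decline after the same dose, C(12 h)/C(24 h) = 2^(12/t½):

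- t½ = 24 h: 2^0.5 = 1.41
- t½ = 12 h: 2^1 = 2.0
- t½ = 6 h: 2^2 = 4.0

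A missed dose acts the other way. C(48 h)/C(24 h) = 2^(−24/t½), which is 0.50, 0.25 and 0.06 at the same half-lives.

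**4. Effect on the group summary.** Assume a share f of evening dosers sampled at 12 hours, with everyone else at 24 hours and otherwise equal. With r the ratio from step 3, the arithmetic mean rises by f(r − 1) and the geometric mean by r^f − 1. For an assumed f = 10%:

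- t½ = 24 h: 0.1 × 0.41 = 4% arithmetic; 1.41^0.1 − 1 = 4% geometric
- t½ = 12 h: 0.1 × 1 = 10% arithmetic; 2^0.1 − 1 = 7% geometric
- t½ = 6 h: 0.1 × 3 = 30% arithmetic; 4^0.1 − 1 = 15% geometric

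**5. What can be recovered.** Usual-time dosing is recorded on visit days at Months 1, 6, 12, 18 and 24. If the habit is regular, a sample drawn g hours before that day's recorded dose was taken about 24 − g hours after the previous one. This is an inference from habit and cannot reveal a missed or shifted dose.

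**6. The SAP's own tolerance applied to 24 hours.** 24 ± 10% = 24 ± 2.4, or 21.6 to 26.4 h.

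**The case against.** The strongest reply is that elapsed time is not lost. Visit-day cards record the usual dosing time on both sides of Month 3, so a habitual evening doser can be identified and time since the last dose approximated. This stands. A reader who concludes that the timing is unrecoverable goes further than the documents allow. What remains is that the actual preceding dose is never observed.

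A reader might also infer that the trough parameter is misread. It is not: SAP section 5 takes C_trough from the 24-hour post-dose sample. (The protocol's abbreviation list ties it to the sample before dosing; that wording needs reconciling separately.) The SAP calls the Month 3 sample pre-dose, which is accurate, and does not label it a steady-state value.

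Nor is there a general bias in Cmax and AUC. These are calculated only for Version 1.0 subjects (Protocol sections 3.2.3 and 8.7, SAP section 5), with full profiles in roughly 20 to 30 (SAP section 7.4). A new dose-card line cannot help Month 3 visits already completed.

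Other limits also stand. Ten of 13 is a worst case, and the stated preference is for mornings. Months 6 to 24 are only listed in the SAP; population PK has its own plan. The eCRF and Laboratory Manual are not in the documents and might capture the previous dose, though neither protocol nor SAP says so. Finally, a strict 21.6 to 26.4 h inclusion rule would drop every completed Month 3 visit without the new record, so exclusion should not be the main analysis.

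**Conclusion.** The gap is real and modest. As written, the plan never asks for the time of the dose before a PK visit, and SAP section 11 applies a time window to post-dose samples but none to the interval before the pre-dose sample. Month 3 pre-dose values from different points in the dosing interval are therefore pooled without a marker, and sparse samples drawn before the day's dose have only an inferred elapsed time.

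The size cannot be determined from the documents. The individual ratios of 1.4 to 4.0 rest on assumed half-lives of 24 to 6 h and mono-exponential decline. The group shifts of about 4% to 30% also rest on an assumed 10% of evening dosers. The primary safety endpoints are untouched. The affected output is the descriptive Month 3 pre-dose summary and plots, the listings at other visits, the input to population PK and, for Version 1.0 subjects only, possibly Cmax and AUC.

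The change is worth making because it captures data that the plan otherwise never collects, at little cost.

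**What to change.** **Data collection.** For all remaining PK visits, add to the dose card and the PK eCRF page the date and time of the last dose taken before the visit. List time since that dose for every sample drawn before the day's dose.

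**SAP section 11.**

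- Keep the Month 3 pre-dose summary in all subjects.
- Flag values whose time since the previous dose falls outside 21.6 to 26.4 h. Use the recorded time where there is one; for completed visits, use the time inferred from the usual dosing time on visit-day cards, and mark it as inferred.
- Repeat the pre-dose summary and the median plot without the flagged values.
- Flag the affected Version 1.0 profiles in the parameter listing.

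**Cost.** One extra data field, one extra summary with its plot, and inferred rather than observed times for visits already completed. Applying the 10% tolerance to the 24-hour interval is a convention borrowed from the post-dose rule, which is why it serves as a flag and a sensitivity summary and does not decide inclusion. No change to dosing is proposed.
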